3.2 Outcome Variables

For each patient, an overall RECIST visit response of CR, PR, SD, PD, NED, NE, will be determined from the BICR as described in Section 3.1.4 above. The outcome variables involving RECIST data, i.e. PFS, best overall response, ORR and DCR, will be derived using overall visit responses and relevant dates from the BICR (which is considered to be the primary RECIST dataset), unless otherwise stated.

Separately, investigator-assessed site measurements/assessments (TLs, NTLs, new lesions) will be used to programmatically derive an investigator assessment of overall visit response.

3.2.1 Progression-Free Survival

Progression-free survival is defined as the time from randomisation until the date of objective radiological disease progression according to modified RECIST or death (by any cause in the absence of disease progression) regardless of whether the patient withdraws from randomised therapy or receives another anticancer therapy prior to disease progression (i.e. date of RECIST progression/death or censoring – date of randomisation + 1). Patients who have not progressed or died at the time of analysis will be censored at the time of the latest date of assessment from their last evaluable RECIST assessment. However, if the patient progresses or dies after two or more missed visits, the patient will be censored at the time of the latest evaluable RECIST assessment (prior to the missing visits). Given the scheduled visit assessment scheme, for the first 40 weeks from randomisation, two missing visits will equate to more than 18 weeks since the previous RECIST assessment, allowing an extra two weeks for early and late visits. After 40 weeks, two missing visits will equate to more than 26 weeks. If two missed visits occur over the period when the scheduled frequency of RECIST assessments changes (ie, from every 8 weeks to every 12 weeks), this will equate to more than 22 weeks (allowing for an early assessment at Week 32 and a late assessment at Week 52). Please refer to the appendix for a graphical display of the allowed time gap in RECIST assessments ([Appendix D: Visualisation of Censoring Rule for Progression Free Survival](#)).

The baseline RECIST assessment should be performed prior to randomisation but if an evaluable RECIST assessment occurs after randomisation but before treatment then this assessment will be used as the baseline assessment. If the patient has no evaluable visits or does not have a baseline assessment, they will be censored at day 1 unless they die within two tumour assessment visits of randomisation (16 weeks plus 1 week allowing for a late assessment within the visit window).

If a patient has two missing visits between two evaluable RECIST assessments with outcome not equal to progression at the second evaluable RECIST assessment, but then subsequently progresses, the patient will not be censored when analysing for PFS. For example, if RECIST assessments were performed at week 8 with outcome SD, week 32 with outcome SD and week 40 with a progression event (weeks 16 and 24 were missed), the patient will be analysed from time of randomisation until progression event at week 40 without considering the interruptions.

The PFS time will always be derived based on scan/assessment dates not visit dates.

The RECIST assessments/scans contributing towards a particular visit may be performed on different dates. The following rules will be applied:

- (a) For BICR data, the date of progression will be determined based on the earliest of the scan dates of the component that triggered the progression for the adjudicated reviewer selecting PD or of either reviewer where both select PD as a time point response and there is no adjudication.

- (b) For investigational site assessments, date of progression will be determined based on the earliest of the RECIST assessment/scan dates of the component that triggered the progression.
- (c) For both BICR data and investigational site assessments, when censoring a patient for PFS, the patient will be censored at the latest of the RECIST assessment/scan dates contributing to a particular overall visit assessment.

Overall visit assessments will be determined by the investigator and BICR for each assessment (scheduled or unscheduled) and will contribute to the derivation of PFS.

Objective progression is defined as at least a 20% increase in the sum of the diameters of the TLs (compared to previous minimum sum) and an absolute increase of > 5 mm, or an overall NTLs assessment of progression or a new lesion.

The primary analysis will be based on the programmatically derived PFS based on the BICR of the radiological scans, and using all scans regardless of whether they were scheduled or not. A sensitivity analysis based on the derived PFS based on investigator-recorded assessments will be carried out.

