3.1 Derivation of RECIST Visit Responses

Patients with measurable or non-measurable disease or NED assessed at baseline by computed tomography (CT) / magnetic resonance imaging (MRI) will be entered in this study. RECIST has been modified to allow the assessment of progression due to new lesions in patients with NED at baseline (inclusion criteria #4).

For all patients, the RECIST tumour response data will be used to determine each patient's visit response according to modified RECIST version 1.1. It will also be used to determine if and when a patient has progressed in accordance with RECIST and also their best overall response.

Baseline radiological tumour assessments are to be performed no more than 28 days before start of study treatment and ideally as close as possible to the start of study treatment and prior to randomisation. Tumour assessments are then performed every 8 weeks (± 1 week) up to 40 weeks and then every 12 weeks (± 1 week) following randomisation until disease progression.

If an unscheduled assessment was performed and the patient had not progressed, every attempt should be made to perform the subsequent assessments at their scheduled visits. This schedule is to be followed in order to minimise any unintentional bias caused by some patients being assessed at a different frequency than other patients.

At each visit, an overall visit response will be provided by the BICR and separately by the investigator - using the information from target lesions (TL), non-target lesions (NTL) and new lesions.

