Appendix D: Visualisation of Censoring Rule for Progression Free Survival

TAKE LAST EVALUABLE ASSESSMENT AND THEN LOOK FORWARD

(1) Last evaluable assessment on or prior to Week 25 then interval to consider is 126 days

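### The 126-day form of the PFS missed-visit rule has no exception for a baseline scan, so a week-16 progression after one missed visit can be censored

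*SAP*

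**What the plan says.** Section 3.2.1 of the SAP states the trigger in terms of visits: "if the patient progresses or dies after two or more missed visits, the patient will be censored at the time of the latest evaluable RECIST" scan, meaning the one before the gap. It then gives the working definition for the first 40 weeks, "two missing visits will equate to more than 18 weeks since the previous RECIST assessment", and explains the margin as "allowing an extra two weeks for early and late visits". Appendix D, to which 3.2.1 refers, starts from the last evaluable assessment and looks forward. Its one legible branch reads "Last evaluable assessment on or prior to Week 25 then interval to consider is 126 days". The rest of that figure is not shown.

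On the baseline scan, section 3.1 says "Baseline radiological tumour assessments are to be performed no more than 28 days before start of study treatment", ideally as close as possible to the start of treatment. Section 3.2.1 adds "The baseline RECIST assessment should be performed prior to randomisation", but accepts a scan after randomisation if it precedes treatment. Follow-up scans are due every 8 weeks (±1 week) to week 40, counted from randomisation.

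One further rule in 3.2.1 counts from randomisation. Patients with no evaluable visit, or with no baseline, are "censored at day 1 unless they die within two tumour assessment visits of randomisation", which the section sets at 16 weeks plus 1 week.

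**The concern.** The trigger counts visits, whereas the definition to be programmed counts days from the previous scan. The two agree when the previous scan is an on-study visit that can be at most a week early. A baseline scan is not such a visit: it can precede randomisation by up to four weeks, and nothing legible in 3.2.1 or Appendix D stops it from being the previous assessment.

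A patient with one missed visit can therefore be handled as having missed two, depending on when the screening scan was taken. A true early progression would then drop out of the primary event set. The same derivation serves investigator-assessed PFS at DCO2. It also reaches PFS2 where section 3.2.3 refers back to 3.2.1 for deaths without any progression, and best response through section 3.2.7, which leaves out progressions censored in this way.

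**Working it through.** **The plan's own figures.** 2 × 8 + 1 + 1 = 18 weeks = 126 days. The companion figures also reproduce: 2 × 12 + 2 = 26 weeks; 53 − 31 = 22 weeks across the change of frequency; 2 × 8 + 1 = 17 weeks = 119 days for deaths. The figures are sound for the gaps they were built for.

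**Gap from a baseline scan.** Let L be the days from baseline scan to randomisation and d the days from randomisation to the scan showing progression. Week 8 is missed or not evaluable. The event is lost when L + d > 126.

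| Week-16 scan | d | Gap at L = 28 | Lost when L exceeds |
|---|---|---|---|
| one week early | 105 | 133 | 21 |
| on time | 112 | 140 | 14 |
| one week late | 119 | 147 | 7 |

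With L = 28 the allowance ends 126 − 28 = 98 days after randomisation, before the week-16 window (days 105 to 119) opens.

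**If treatment starts after randomisation.** The 28-day limit runs to first dose, so a delay of g days caps L at 28 − g. An on-time event can still be lost for g up to 13 days, a late one for g up to 20 and an early one for g up to 6. The schedule in Appendix C places randomisation on Day 1, which corresponds to g = 0.

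**Censoring date.** The last evaluable assessment before the gap is the baseline, which precedes randomisation. PFS time is the censoring date minus the randomisation date plus 1, so it would be zero or negative for L of 1 day or more. The reset to day 1 is written only for patients with no evaluable visit or no baseline. This patient has an evaluable scan, the one showing progression.

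**Deaths.** For a patient with no evaluable post-baseline visit and L = 28, a death 99 to 119 days after randomisation is an event under the 17-week rule but is censored under 126 days from baseline. The SAP does not say which rule prevails.

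**Rough size.** Neither baseline timing nor week-8 missingness is in the documents, so both are assumed.
- Share of such week-16 progressions lost, with d even over 105 to 119 and L even over 0-14, 0-21 or 0-28 days: 12.5%, 33% or 50%.
- Planned patients: 145 × 2/5 = 58 placebo and 145 × 3/5 = 87 olaparib. Planned medians: 4 and 4 + 3.4 = 7.4 months, exponential. PFS events by week 16: 47.1% and 29.2%, so 58 × 0.471 + 87 × 0.292 ≈ 53.
- Low: 53 × 5% × 33% ≈ 0.9. High: 53 × 10% × 50% ≈ 2.6. That is about 1 to 3 of 87 events.

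**The case against.** The strongest reply is that the operative condition is two missed visits. On that view the day count only translates the condition under a schedule that runs from randomisation, so one missed visit never satisfies it. A pre-randomisation censoring date also suggests that the literal result was not intended. This is a fair account of the intent, but PFS is derived programmatically, and the legible programming instruction is the day count. Where the two disagree, the text does not say that the visit count wins.

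The unseen part of the Appendix D figure could contain a baseline branch. That stands as a caveat, although the prose of 3.2.1 contains none.

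The attrition-bias analysis in section 4.2.2.1 puts these events back at their actual times, with a by-patient listing of progressions censored for missed assessments. This is real mitigation. It does not isolate the problem, because the same analysis also censors at subsequent therapy, and the primary analysis is unchanged.

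The size estimate leans high. Scans are meant to be close to treatment start, the 53 includes deaths, and an unscheduled evaluable scan would close the gap. All of that stands. DCO1 has also passed, and the remaining PFS analysis at DCO2 is descriptive.

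Three stronger readings are tempting and are not supported. A reader might infer that these patients are censored at day 1, but the SAP states no such reset for them. A reader might infer that anyone who misses week 8 is exposed, but the loss needs the baseline leads shown above. A reader might suspect a bias towards olaparib. Under the planned medians, relatively more placebo patients have an event by week 16 (47% against 29%), so losing such events would more likely weaken the observed effect.

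**Conclusion.** The point holds as a conflict between the visit-based trigger and its day count when the previous assessment is the baseline. Read literally, the rule censors a week-16 progression after a single missed visit once baseline precedes randomisation by more than 14 days (more than 7 if the scan is a week late, more than 21 if a week early). It leaves the censoring date undefined in any usable sense and can contradict the 17-week rule for deaths.

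The number of events affected cannot be derived from the documents. The range of about 1 to 3 rests wholly on the assumed missingness and baseline timing, and with all leads within 14 days it would be lower. No effect on the hazard ratio has been shown. The text should be corrected, but nothing here gives reason to doubt the direction of the primary result.

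**What to change.** In 3.2.1 and Appendix D, state that when the last evaluable assessment is the baseline, whether taken before or after randomisation, two missed visits means more than 17 weeks (119 days) after randomisation, for progression and death alike, with censoring at day 1. State that the 126-day interval starts only from post-baseline assessments. Every week-16 progression within its visit window is then kept, whatever the baseline date, and a baseline taken after randomisation falls under one clause only.

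Apply this to investigator-assessed PFS at DCO2 and to the PFS2 branches that refer to 3.2.1. Leave the DCO1 primary result as analysed, and report by arm how many BICR events the literal rule censored there. The attrition listing is a starting point for that count.

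The cost is one sentence and a small change to the derivation code. There is a trade-off: with a baseline 0 to 6 days before randomisation, the present rule keeps some events on days 120 to 126 (slightly later if baseline followed randomisation), and these would now be censored. The DCO2 derivation would also differ slightly from DCO1, which should be flagged in the report.

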3.1.1 Target lesions

Measurable disease is defined as having at least one measurable lesion, not previously irradiated, which is ≥ 10 mm in the longest diameter (except lymph nodes which must have

short axis ≥ 15 mm) with CT or MRI and which is suitable for accurate repeated measurements.

A patient can have a maximum of 5 measurable lesions recorded at baseline with a maximum of 2 lesions per organ (representative of all lesions involved suitable for accurate repeated measurement) and these are referred to as TLs. If more than one baseline scan is recorded, then measurements from the one that is closest to and prior to randomisation will be used to define the baseline sum of TLs. It may be the case that, on occasion, the largest lesion does not lend itself to reproducible measurement in which circumstance the next largest lesion, which can be measured reproducibly, should be selected.

All other lesions (or sites of disease) not recorded as TLs should be identified as NTLs at baseline. Measurements are not required for these lesions, but their status should be followed at subsequent visits.

Note: For patients who do not have measurable disease at entry (ie, no TLs) but have non-measurable disease, evaluation of overall visit responses will be based on the overall NTLs assessment and the absence/presence of new lesions (see [Section 3.1.3](#) of the Clinical Study Protocol (CSP) for further details). If a patient does not have measurable disease at baseline, then the TL visit response will be not applicable (NA).

For patients with NED at baseline (ie, no TLs and no NTLs), evaluation of overall visit responses will be based on absence/presence of new lesions. If no TLs and no NTLs are recorded at a visit, both the TL and NTL visit response will be recorded as NA and the overall visit response will be NED.

Table 3 TL Visit Responses

Visit Responses	Description
CR	Disappearance of all TLs since baseline. Any pathological lymph nodes selected as TLs must have a reduction in short axis to <10 mm.
PR	At least a 30% decrease in the sum of diameters of TLs, taking as reference the baseline sum of diameters.
SD	Neither sufficient shrinkage to qualify for PR nor sufficient increase to qualify for PD.

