PD	At least a 20% increase in the sum of diameters of TLs, taking as reference the smallest sum on study (this includes the baseline sum if that is the smallest on study). In addition to the relative increase of 20%, the sum must also indicate an absolute increase of at least 5 mm.
NE	Only relevant if any of the TLs were not assessed or not evaluable or had a lesion intervention at this visit. Note: If the sum of diameters meets the PD criteria, PD overrides NE as a TL response.
NA	No TLs are recorded at baseline.

Rounding of TL data

For calculation of PD and PR for TLs, percentage changes from baseline and previous minimum should be rounded to 1 decimal place before assigning a TL response. For example 19.95% should be rounded to 20.0% but 19.94% should be rounded to 19.9%.

Missing TL data

For a visit to be evaluable, all TL measurements should be recorded. However, a visit response of PD should still be assigned if any of the following occurred:

- A new lesion is recorded.
- A NTL visit response of PD is recorded.
- The sum of TLs is sufficiently increased to result in a 20% increase, and an absolute increase of ≥ 5 mm from nadir, even assuming the non-recorded TLs have disappeared. Note: the nadir can only be taken from assessments where all the TLs had a longest diameter (LD) recorded, including non-missing TLs which have had intervention during the study and prior to any scaling of the measurements.

If there is at least one TL measurement missing and a visit response of PD cannot be assigned, the visit response is NE.

Lymph nodes

For lymph nodes, if the size reduces to < 10 mm then these are considered non-pathological. However, a size will still be given, and this size should still be used to determine the TL visit response as normal. In the special case where all lymph nodes are < 10 mm and all other TLs are 0 mm, then although the sum may be > 0 mm the calculation of TL response should be over-written as a CR.

TL visit responses subsequent to CR

A CR can only be followed by CR, PD or NE. If a CR has occurred then the following rules at the subsequent visits must be applied:

- Step 1: If all lesions meet the CR criteria (ie, 0 mm or < 10 mm for lymph nodes) then response will be set to CR irrespective of whether the criteria for PD of TL is also met ie, if a lymph node LD increases by 20% but remains < 10 mm.

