If the question ‘Any new lesions since baseline’ has not been answered with Yes or No and the new lesion details are blank this is not evidence that no new lesions are present and should be treated as NE in the derivation of overall visit response.

‘Symptomatic deterioration’ is not a descriptor for progression of NTLs: it is a reason for stopping study therapy and will not be included in any assessment of NTLs. Patients with symptomatic deterioration requiring discontinuation of treatment without objective evidence of disease progression at that time should continue to undergo tumour assessments where possible until objective disease progression is observed.

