3.1.3 Overall visit response

Table 6 defines how the previously defined TL and NTL visit responses will be combined with new lesion information to give an overall visit response.

Table 6 Overall Visit Responses

Target lesions	Non-target lesions	New lesions	Overall response
CR	CR or NA	No (or NE)	CR
NA	CR	No (or NE)	CR
CR	Non-CR/Non-PD or NE	No (or NE)	PR
PR	Non-PD or NE or NA	No (or NE)	PR
SD	Non-PD or NE or NA	No (or NE)	SD
NA	Non-CR/Non-PD	No (or NE)	SD
NE	Non-PD or NE or NA	No (or NE)	NE
NA	NE	No (or NE)	NE
PD	Any	Any	PD
Any	PD	Any	PD
Any	Any	Yes	PD
NA	NA	No (or NE)	NED

NA is only relevant if there were no TL/NTL at baseline.

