3.2.3 Time from randomisation to second progression

The time from randomisation to second progression (PFS2) is defined as the time from the date of randomisation to the earliest of the second progression event as assessed by the investigator or death (ie date of PFS2 event or censoring – date of randomisation + 1). The

date of second progression will be recorded by the investigator and defined according to local standard clinical practice and may involve any of objective radiological or symptomatic progression or death. The RECIST assessments will not be collected for assessment of PFS2. The date of the PFS2 assessment and investigator opinion of progression status (progressed or non-progressed) at each assessment will be recorded in the eCRF.

Second progression status will be reviewed every 8 weeks following the investigator assessment of the first objective progression and status recorded (until DCO2). Patients alive and for whom a second disease progression has not been observed should be censored at the last time known to be alive and without a second disease progression, ie, censored at the latest of the RECIST assessment or PFS2 assessment dates. If a patient progresses for the second time or dies after two or more missed visits, the patient will be censored for PFS2 at the time of the latest evaluable investigator – recorded assessment.

Censoring will need to be applied for some patients prior to the first progression and for others after the first progression, depending if the patient had a first progression at the time of analysis or not. The duration of two missed visits is depending on the respective visit schedule:

- If the patient was progression-free at the time of analysis, then patients will be censored as described for PFS (Section 3.2.1), i.e. using the latest RECIST scan.
- If the patient died in the absence of any progression after two or more missed visits, then the censoring visit rule as described for PFS (Section 3.2.1) needs to be applied.
- If a patient is alive and had only the first progression assessed at the time of analysis, then the censoring will be based on the latest investigator assessment of no progression in the follow-up phase. If there are no follow-up results recorded, then the date of the latest scan contributing to the investigator assessment of first progression will be used for censoring.

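### Minor: Table 6 makes a blank new-lesion item a progression-free visit for patients with no disease at baseline, and Section 3.2.1 states the 5 mm progression threshold differently from Table 3

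*SAP*

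**What the plan says.** **How the investigator response is produced.** Section 3.2 says that the site's lesion data "will be used to programmatically derive an investigator assessment of overall visit response". The response tables in Section 3.1 are therefore programming rules.

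**Patients with no disease at baseline.** Under Section 3.1.1, for patients with neither target nor non-target lesions, "evaluation of overall visit responses will be based on absence/presence of new lesions". Section 3.1.2 covers the case where the new-lesion question is unanswered and the lesion details are blank. It says that "this is not evidence that no new lesions are present and should be treated as NE in the derivation of overall visit response". The last row of Table 6 (Section 3.1.3), in the order target, non-target, new lesions, overall, reads "NA NA No (or NE) NED". Section 3.1.4 lists PD, NED and NE as the BICR categories for patients with no disease at baseline.

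**Progression threshold.** For target lesions, Table 3 in Section 3.1.1 adds to the 20% rise that "the sum must also indicate an absolute increase of at least 5 mm". The missing-data rule in the same section is also inclusive at 5 mm. Section 3.2.1, defining objective progression for PFS, asks instead for "an absolute increase of > 5 mm, or an overall NTLs assessment of progression or a new lesion".

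**Where evaluable visits matter.** Section 3.2.1 says that "if the patient progresses or dies after two or more missed visits, the patient will be censored at the time of the latest evaluable RECIST" evaluation before the gap. Appendix D sets the gap at 126 days when the last evaluable assessment is at or before week 25. Section 3.2.3 carries the rule into PFS2: for a patient who "died in the absence of any progression after two or more missed visits, then the censoring visit rule as described for PFS" is to be applied.

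**The concern.** In the CR, PR and SD rows of Table 6, a target or non-target finding supports the response, so tolerating an unevaluable new-lesion item is defensible there. In the last row nothing else supports it. With both lesion components not applicable and new lesions NE, the visit holds no recorded evidence, yet the program returns NED, an evaluable and progression-free result.

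Three investigator outputs can change:

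- **PFS.** The blank visit becomes the latest evaluable assessment. That can turn a censored patient into an event, or move a censoring date later. Investigator PFS is a sensitivity analysis at DCO1 and a descriptive analysis at DCO2 (Section 4.2.2). Some PFS2 censoring follows through Section 3.2.3.
- **Best response.** Section 3.2.7 ranks NED above PD and NE, so a blank visit can be credited as the best response.
- **Disease control.** Section 3.2.9 counts NED held for at least 15 weeks.

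The 5 mm wording is a separate and smaller matter. At one exact value, the SAP gives two answers to whether a visit is progression.

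**Working it through.** The SAP states no figure for either rule, so there is none to reproduce. The check applies the rules as written.

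**Table 6.** I crossed every target category (CR, PR, SD, NE, NA, PD) with every non-target category (CR, non-CR/non-PD, NE, NA, PD) and compared new lesions = No with new lesions = NE.

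- The overall response differs in 0 cells, so the NE assigned in Section 3.1.2 never changes a result.
- For NA/NA: No gives NED, NE gives NED, Yes gives PD. NE cannot be reached, although Section 3.1.4 allows it to the BICR for these patients.

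**Effect on the censoring clock.** The limit from Section 3.2.1 and Appendix D is more than 18 weeks, and 18 × 7 = 126 days. Visits fall at week 8 = day 56, week 16 = day 112, week 32 = day 224 and week 40 = day 280. The extra day in the PFS formula does not alter gaps. Take NED at week 8, a blank at week 16, week 24 missed and an event at week 32.

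| Week 16 counted as | Last evaluable | Gap to day 224 | Result |
|---|---|---|---|
| NED (Table 6 as written) | day 112 | 224 − 112 = 112 ≤ 126 | event at week 32 |
| NE | day 56 | 224 − 56 = 168 > 126 | censored at week 8 |

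In this pattern, status flips for a death after day 56 + 126 = 182 and up to day 112 + 126 = 238. That is days 183 to 238, or 238 − 182 = 56 days. A progression found at a scheduled scan flips only at week 32. At week 40 the gap from week 16 is 280 − 112 = 168 > 126, so the patient is censored either way and only the censoring date differs.

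**Effect on disease control.** Take NED at week 8, a blank at week 16 and progression at week 24. Under Table 6, NED is held to week 16, and 16 ≥ 15, so disease control is credited. With week 16 as NE, the last NED is week 8, and 8 < 15, so it is not.

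**Progression threshold.** The rules can differ only when the rise is exactly 5 mm and also reaches 20%.

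- Unrounded: 5 / n ≥ 0.20 gives n ≤ 5 / 0.20 = 25 mm.
- With the one-decimal rounding in Section 3.1.1 (19.95% counts as 20.0%): n ≤ 5 / 0.1995 = 25.06 mm.
- Over whole-millimetre nadir sums of 1 to 200 mm, the rules disagree in 25 cases: nadir 1 to 25 mm, each with a rise of exactly 5 mm.
- Example: 25 to 30 mm (20.0%, +5 mm) is PD under Table 3 and not under Section 3.2.1. From a nadir of 26 mm, both first call PD at 32 mm.

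Even then, the visit must have no non-target progression and no new lesion for the difference to matter.

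**The case against.** Four points can be made for the plan as it stands.

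- **Sections 3.1.2 and 3.1.3 can be read together.** A reader might infer that they contradict each other. The natural reading of Section 3.1.2 is that the blank item enters the derivation as NE, and Table 6 has a place for that input. Section 3.1.1 also says that with no target and no non-target lesions recorded the overall response is NED. This stands: the fault is a poor convention. It remains a fault, because the convention treats a missing answer as a negative one where that answer is the only evidence.
- **A blank item is an incomplete form entry.** It does not show that the scan was unreadable. This also stands, but the program sees only the form, and Section 3.1.2 itself declines to take the blank as a negative.
- **The strict 5 mm wording is probably not operative.** Visit responses come from Table 3 through Table 6, and PFS is built from visit responses. Section 3.2.1 reads as a loose summary. This stands, and makes the symbol a boundary correction.
- **The primary result is not at risk.** Because the strict wording sits in the section defining the primary endpoint, a reader might infer that BICR PFS is in doubt. The SAP does not support that: under Section 3.1.4 the BICR supplies its own overall visit responses, with NE available for patients without baseline disease.

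**Conclusion.** The point holds as a minor one. The last row of Table 6 is a wrong rule for visits without a new-lesion answer in patients with no baseline disease, and the 5 mm threshold is stated in two ways. Both act on investigator-derived outputs: PFS, best response and disease control, with some PFS2 censoring. No confirmatory test is affected.

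The number of patients affected cannot be derived, because the SAP gives neither the share with no disease at baseline nor the rate of unanswered new-lesion items. It is probably very small. A change of event status through Table 6 needs no baseline disease, a blank item, a gap in assessments and an event inside a limited window. The 5 mm difference needs one exact value on a small lesion sum. The example assumes scans on their nominal weeks and that an NE visit counts as missed. The latter fits Section 4.2.2.1, which describes the patients censored by the primary rule in terms of non-evaluable assessments.

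**What to change.** - **Table 6.** Split the last row: NA/NA with new lesions No gives NED; NA/NA with new lesions NE gives NE. The statement in Section 3.1.1 that the response is NED when no lesions are recorded must follow the split row.
- **Section 3.1.2.** State that NE there means the new-lesion component, with the overall response then read from Table 6.
- **Section 3.2.1.** Change the strict 5 mm threshold to the inclusive one in Table 3, from which visit responses are derived.
- **DCO1.** Record which rules were programmed. DCO1 took place on 15 January 2019 and the study was unblinded for that analysis, so the record guards against a patient's status changing between cut-offs through a later choice of rule. This also suffices for best response, which Table 10 lists at DCO1 and not at DCO2, and for disease control, which is only summarised.
- **DCO2.** List any patient whose investigator PFS status or date differs between the rules, and repeat investigator PFS only if there is one. A routine second run of PFS or PFS2 is not needed.

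The cost is one table row, one symbol, a sentence or two, a note to file and one listing, plus at most one repeat analysis. The DCO1 primary result stays unchanged.
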